7.4.2.2 Dose Interruptions

Each study therapy may be interrupted. This information will be retrieved from CRF dosing pages. (For capecitabine and S-1, which are oral, interruption will be programmatically derived.)

The following parameters will be summarized by treatment arm:

- Number of subject with at least one dose infusion interrupted along with reason for the interruptions and number of infusions interrupted per subject

7.4.2.3 IV Rate Reductions

For each study therapy dosed as IV (BMS-986213, nivolumab, oxaliplatin, leucovorin, and fluorouracil) IV rate may be reduced. This information will be retrieved from CRF dosing pages.

The following parameters will be summarized by treatment arm:

- Number of subject with at least one IV rate reduction along with reason for the IV rate reduction and number of infusions with IV rate reduced per subject

7.4.2.4 Dose Escalations

Dose escalations of BMS-986213 or nivolumab are not permitted.

7.4.2.5 Dose Reductions

Dose reductions of BMS-986213 or nivolumab are not permitted.

7.4.2.6 Dose Omissions

Dose reductions of BMS-986213 or nivolumab are not permitted.

7.4.3 Concomitant Medications

Concomitant medications, defined as medications other than study medications which are taken at any time on-treatment (i.e. on or after the first day of study therapy and within 100 days following the last dose of study therapy), will be coded using the UMC WHO Drug Global Dictionary.

The following summary table will be provided:

- Concomitant medications (subjects with any concomitant medication, subjects by medication class and generic term)

The following summary table will be provided:

- Prior/current medications (subjects with any prior/current medication, subjects by medication class and generic term)

A by-subject listing(s) will accompany the table(s).

7.4.3.1 Immune Modulating Medication

Immune modulating concomitant medications are medications entered on an immune modulating medication form or available from the most current pre-defined list of immune modulating medications. The list of anatomic class, therapeutic class and generic name used for the selection at the time of the database lock will be provided.

The percentage of subjects who received immune modulating concomitant medication for

- management of adverse event
- premedication
- other use
- any use
- management of drug-related select adverse event (any grade, grade 3-5) by select AE category/subcategory (EU/ROW Submissions)
- management of IMAEs (any grade, grade 3-5) by IMAE category (US Submission) will be reported separately for each treatment group (percentages of treated subjects by medication class and generic term).

For each category/subcategory of drug-related select AEs (any grade, grade 3-5) and IMAEs (any grade, grade 3-5), the following will be reported for each treatment group:

- The total immune modulating medication treatment duration (excluding overlaps), duration of high dose of corticosteroid, initial dose of corticosteroid, and tapering duration (summary statistics)

Duration represents the total duration the subject received the concomitant medication of interest. If the subject took the medication periodically, then DURATION is the summation of all use. Initial dose represents the dose of the concomitant medication of interest received at the start of the event. In the case multiple medications started on the same date, the highest equivalent dose is chosen and converted to mg/kg by dividing by the subject's recent weight.

These analyses, except the ones related to IMAEs will be conducted using the 30-day safety window. The analyses related to IMAEs will be conducted using the 100-day safety window.

7.4.3.2 Subsequent Cancer Therapy

- Number and percentage of subjects receiving subsequent therapies will be summarized. Categories include:
 - Immunotherapy including commercial Nivolumab (anti-PD1 agents, anti-PD-L1 agents, anti-CTLA-4 agents and others) by drug name
 - Other anti-cancer agents excluding all immunotherapy (approved and investigational) by drug name
 - Surgery for treatment of tumors
 - Radiotherapy for treatment of tumors
 - Any combination of the above
- A subject listing of follow-up therapy will also be produced for subjects who had any subsequent therapy

7.5 Efficacy

Principal analyses of objective response rate (ORR) and progression free survival (PFS) will be based on the Blinded Independent Central Review (BICR) evaluation, unless noted otherwise.

Unless stated otherwise, whenever a stratified analysis is specified in the all randomized population, the following stratifications factors (recorded at randomization as per IRT) will be used, except for the analysis in LAG-3 positive or LAG-3 negative sub-groups when only PDL1 CPS expression will be used.

- LAG-3 expression ($\geq 1\%$ or $< 1\%$; no indeterminate allowed)
- PD-L1 expression status (CPS ≥ 5 , CPS ≥ 1 to < 5 , CPS < 1 or indeterminate)

There will be no p-values presented for any of the analyses other than the primary endpoint. All other analyses will be descriptive in nature. Confidence intervals for all endpoints will be at the two-sided 95% level. Point estimates and confidence bounds for efficacy variables will be rounded to the second decimal place.

7.5.1 Analysis of Objective Response Rate (ORR)

Primary (and secondary) objectives of the study are to compare ORR per BICR between treatment groups among LAG-3 positive (primary objective) and among LAG-3 negative (secondary objective) randomized subjects.

[figure not shown]
The number and percentage of subjects in each category of BOR per BICR (complete response [CR], partial response [PR], stable disease [SD], progressive disease [PD], or unable to determine [UTD]) will be presented, by treatment group, for each LAG-3 population and overall. Estimates of response rate, along with its exact two-sided 95% CI by Clopper and Pearson¹¹ will be presented, by treatment group for each LAG-3 population and overall.

[figure not shown]
ORR as assessed by BICR will be compared between treatment groups using a two-sided Cochran-Mantel-Haenszel test stratified by PD-L1 status ((CPS $\geq 5\%$, CPS ≥ 1 to <5 , or CPS $< 1\%$ (including indeterminate)) as recorded in the IRT. These analyses and associated 70% CIs for ORR difference will be performed on the All Randomized LAG-3 Positive Subjects (primary population), All Randomized LAG-3 Negative Subjects, and All Randomized Subjects.

The following subject-level graphics will also be provided:

- For the responders only, time courses of the following events of interest will be graphically displayed: tumor response, progression, last dose received, and death
- For response evaluable subjects (defined per RECIST 1.1 as randomized subjects with baseline and at least one on-study tumor assessment)
 - A bar plot showing the best % reduction from baseline in sum of diameter of target lesions based on BICR assessment for each subject will be produced (excluding assessments after PD and assessments after start of subsequent anti-cancer therapy)
 - A plot of individual time course of tumor burden change per BICR assessment will be produced

Similar analyses will be repeated based on the investigator's assessment of ORR. A cross tabulation of BICR best response versus the investigator best response will be presented, by treatment group and by response categories. Concordance Rate of Responders will be computed as the frequency with which investigator and BICR agree on the classification of a subject as responder vs. non responder/UTD as a proportion of the total number of randomized subjects (using relevant populations) assessed by both the investigator and BICR.

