6.2.1 Stratification

The randomization will be stratified by the following factors:

- LAG-3 expression ($\geq 1\%$ or $< 1\%$; no indeterminate allowed)
- PD-L1 expression status (CPS ≥ 5 , CPS ≥ 1 to < 5 , CPS < 1 or indeterminate).

Note: region (Japan/Taiwan [J/T] vs Rest of world [ROW]) was originally a stratification factor for the study, but no one from Japan/Taiwan enrolled in the study. Therefore, although it is still in the system as a stratification factor for the study, it will not be analyzed nor used as such.

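### SAP 7.5.1 stratifies the all-randomized ORR comparison by PD-L1 alone, omitting LAG-3, which is a randomization factor and is used for overall PFS and OS

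*SAP*

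**What the plan says.** SAP 6.2.1 introduces the randomization factors with "The randomization will be stratified by the following factors" and lists LAG-3 expression and PD-L1 CPS in three levels. Region is set aside because nobody from Japan or Taiwan enrolled: "although it is still in the system as a stratification factor for the study, it will not be analyzed nor used as such".

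SAP 7.5 sets the general rule: "whenever a stratified analysis is specified in the all randomized population, the following stratifications factors (recorded at randomization as per IRT) will be used". The two factors listed under it are LAG-3 and PD-L1. The rule makes one exception, which concerns analyses inside a single LAG-3 group: "except for the analysis in LAG-3 positive or LAG-3 negative sub-groups when only PDL1 CPS expression will be used". It also opens with a qualifier that lets a later section specify something different.

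SAP 7.5.1 then specifies the ORR comparison: "ORR as assessed by BICR will be compared between treatment groups using a two-sided Cochran-Mantel-Haenszel test stratified by PD-L1 status". On populations it says: "These analyses and associated 70% CIs for ORR difference will be performed on the All Randomized LAG-3 Positive Subjects (primary population". The sentence continues with the randomized LAG-3 negative subjects and all randomized subjects. The same analyses are repeated on investigator assessment.

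SAP 7.5.4 calls for a stratified log-rank test of PFS in all randomized subjects without naming factors, so the 7.5 rule supplies both. SAP 7.5.7 uses the PFS factors for OS.

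Protocol 10.3.2 stratifies overall ORR by region and PD-L1, without LAG-3. In the same table it adds LAG-3 explicitly for overall OS and overall PFS.

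**The concern.** One sentence in SAP 7.5.1 covers three populations that need different strata. Within a LAG-3 group LAG-3 is constant, so PD-L1 alone is correct. Across all randomized subjects LAG-3 varies and was balanced by design, and an analysis that ignores it gives up whatever precision it could supply. A programmer cannot tell whether the omission is intended or whether sub-group wording was carried over to the overall population.

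At stake is the reported interval for a named secondary objective, overall ORR by BICR and by investigator. Overall ORR would also be stratified differently from overall PFS and OS. SAP 7.5.1 names no estimator for the interval and does not say whether the difference is stratified, so the overall result cannot be reproduced from the text as it stands.

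**Working it through.** **The texts side by side**

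| Analysis in all randomized subjects | Protocol 10.3.2 | SAP |
|---|---|---|
| ORR | region, PD-L1 | PD-L1 (7.5.1) |
| PFS | region, PD-L1, LAG-3 | LAG-3, PD-L1 (7.5.4, by the 7.5 rule) |
| OS | region, PD-L1, LAG-3 | LAG-3, PD-L1 (7.5.7, as for PFS) |

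ORR is the only one of the three without LAG-3.

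**Inputs for the size**

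- From the documents: about 250 randomized 1:1 (Protocol 10.1, SAP 5) and a 70% two-sided interval, so z = 1.0364.
- Assumed, because the visible text gives neither LAG-3 prevalence nor any LAG-3 effect on ORR: mean ORR 50%, no treatment effect, half LAG-3 positive, CPS levels split 40/20/40, additive ORR effects, LAG-3 ORR gap of 0 to 30 points.

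The documents state no width for this interval, so there is no planned figure to reproduce.

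**Formula** (only if the interval is a stratified difference)

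Half-width = 1.0364 × √(4V/250), where V is the weighted sum of p(1−p) over strata: three PD-L1 strata without LAG-3, six with it.

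**LAG-3 independent of PD-L1, no PD-L1 effect.** Without LAG-3, V = 0.25 and the half-width is 1.0364 × √0.004 = 6.55 points. With LAG-3, V = 0.25 − gap²/4.

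| LAG-3 gap (points) | V with LAG-3 | Half-width with LAG-3 (points) | PD-L1-only interval wider by |
|---|---|---|---|
| 0 | 0.2500 | 6.55 | 0% |
| 10 | 0.2475 | 6.52 | 0.5% |
| 20 | 0.2400 | 6.42 | 2.1% |
| 30 | 0.2275 | 6.25 | 4.8% |

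**Other assumptions, excess width at gaps of 10/20/30 points**

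| Scenario | No PD-L1 effect | 20-point PD-L1 spread in ORR |
|---|---|---|
| LAG-3 independent of PD-L1 | 0.5 / 2.1 / 4.8% | 0.5 / 2.1 / 5.0% |
| LAG-3 positive in 30/50/70% of the CPS levels | 0.4 / 1.8 / 4.2% | 0.5 / 1.9 / 4.6% |
| LAG-3 positive in 15/50/85% | 0.3 / 1.3 / 3.0% | 0.3 / 1.4 / 3.3% |
| LAG-3 prevalence 30% or 70%, independent | 0.4 / 1.7 / 4.0% | not computed |

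Example (30/50/70%, 30-point gap, no PD-L1 effect): the CPS-level ORRs are 44, 50 and 56%. V = 0.8 × 0.2464 + 0.2 × 0.25 = 0.2471, the half-width is 6.52 points, and 6.517/6.253 = 1.042.

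**Second check.** A large-sample grid with mean ORR 40 to 60%, LAG-3 share 30 to 70% and a 10-point treatment difference gives 0.4–0.5%, 1.7–2.2% and 4.1–5.1% at gaps of 10, 20 and 30 points.

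A simulation used 250 patients, blocked randomization in six strata, CPS split 35/25/40, a 10-point treatment difference and 2,000 runs per scenario. For the Mantel-Haenszel risk difference with the Sato variance it gives about 0%, 0.3–0.5%, 1.3–2.2% and 3.1–5.1% at gaps of 0, 10, 20 and 30 points.

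The Greenland-Robins variance gives 1.2–1.3% at no gap and 4.5–6.5% at 30 points. Its excess at no gap comes from plug-in variances in smaller strata: √[(1 − 3/125)/(1 − 6/125)] = √(0.976/0.952) = 1.0125.

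Simulated coverage of the nominal 70% interval was about 67–73% with PD-L1 alone and 67–71% with both factors.

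**The case against.** The strongest reply is that nothing is breached. The 7.5 rule gives way where a section specifies something different, and 7.5.1 does so. It also follows Protocol 10.3.2, which leaves LAG-3 out of overall ORR. This stands, and it makes the point an inconsistency, not a violation. It does not supply a reason, since the same protocol table adds LAG-3 for overall OS and PFS.

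Second, the omission hardly reaches a reported result. The SAP says "There will be no p-values presented for any of the analyses other than the primary endpoint", so in all randomized subjects only a descriptive interval can change, and only if it is stratified. This also stands and limits the point to minor. No gain in coverage was shown, and the upper figure depends on stopping at a 30-point gap: at 40 points the large-sample grid gives about 7.6 to 9.7%.

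Third, parts of SAP 7.5.1 and of the SAP history are not shown, and the supplied text passes from 7.5.1 to 7.5.3. A reason may lie there. The statement is therefore only that none is visible.

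Fourth, region was dropped because it was empty, whereas adding LAG-3 would create a difference from the protocol that does not exist now, in an open-label trial. That is fair, so the SAP should record the change openly. It is still a refinement of a descriptive secondary analysis using a factor fixed at randomization.

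**Conclusion.** The concern holds and is minor. The overall ORR analysis omits a randomization factor that the SAP's own rule and the overall PFS and OS analyses include, and no reason is visible. Balance on LAG-3 by design means the omission causes no bias and no inflation of type I error, and the primary LAG-3 positive analysis is unaffected.

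The cost is zero if the 70% interval is unstratified. If it is stratified, the loss is about 0 to 5% of width, or 0.30 point (6.55 against 6.25) at a 30-point LAG-3 gap. This rests on the assumed ORR level, LAG-3 prevalence, CPS split and a gap of no more than 30 points, none of which the visible text provides.

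The interval level is a separate matter: SAP 7.5 says "Confidence intervals for all endpoints will be at the two-sided 95% level", while 7.5.1 gives 70%. At 95% the half-width is 12.40 points without LAG-3, against 12.33, 12.15 and 11.82 with it at gaps of 10, 20 and 30 points. The percentages are unchanged.

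**What to change.** In SAP 7.5.1, state that in All Randomized Subjects the CMH test and the interval for the ORR difference, by BICR and by investigator, are stratified by LAG-3 (≥1%, <1%) and PD-L1 CPS (three levels) as recorded in the IRT. State also that within the LAG-3 positive and LAG-3 negative groups they are stratified by PD-L1 CPS only. Name the stratified estimator and its variance, and record that the overall analysis adds a factor not listed for it in Protocol 10.3.2. If leaving LAG-3 out is intended, give the reason instead.

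The cost is a short SAP edit and one more stratum variable in the code, with no new data. Six strata are workable: under the assumed splits the smallest holds 0.2 × 0.5 × 250 = 25 patients, or 0.4 × 0.15 × 250 = 15 if LAG-3 and PD-L1 are strongly correlated. A protocol amendment would need IRB/IEC review and is not warranted for this alone. Align Protocol 10.3.2 if it is amended for other reasons.

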7.5.3 Time to Response and Duration of Response

Duration of response (DOR) and time to response (TTR) will also be evaluated for subjects who achieved confirmed PR or CR. The DOR for each treatment group. The DOR will be estimated using the Kaplan-Meier (KM) product limit method and will be displayed graphically. A table will be produced presenting number of events, number of subjects involved, medians, and 95% CIs for the medians. Median values of DOR, along with two-sided 95% CI in each treatment group will be computed based on a log-log transformation method. These analyses will be performed on the All Randomized LAG-3 Positive Subjects, All Randomized LAG-3 Negative Subjects, and All Randomized Subjects.

The status of subjects who are censored in the DOR KM analysis will be tabulated for each randomized treatment group including the following categories:

- Ongoing follow-up (current [last scan within adequate window vs cutoff date], not current)
- Off-study (lost to follow-up, withdraw consent, never treated)
- Received subsequent anticancer therapy

TTR, which does not involve censoring, will be summarized by treatment group in all responders using descriptive statistics.

- A by-subject listing will be presented including treatment group, time to response, duration of response, whether the subject was censored for duration of response, and, if so, the reason.

Similar analyses will be repeated based on the investigator's assessment of ORR.

7.5.4 Analysis of Progression-Free-Survival

One of the objectives of the study is to assess the difference in progression-free survival (as determined by BICR) between treatment groups in the LAG-3 positive, LAG-3 negative, and all randomized populations.

The analysis of PFS (as determined by BICR) will be to compare the two treatment groups via stratified log-rank test among all randomized subjects at a two-sided $\alpha = 0.30$ level.

The primary definition of PFS adjusting for subsequent anticancer therapy will be used in this analysis.

The estimate of the PFS hazard ratio between treatment groups will be calculated using a stratified Cox proportional hazards model, with treatment as the sole covariate. Ties will be handled using the exact method. A two-sided 70% CI for the hazard ratio will also be presented.

The PFS function for each treatment group will be estimated using the KM product limit method and will be displayed graphically. A two-sided 95% CI for median PFS in each treatment group will be computed via the log-log transformation method.

These estimates will be derived from the Kaplan Meier estimate and corresponding CIs will

be derived based on Greenwood¹⁴ formula for variance derivation and on log-log transformation applied on the survivor function¹⁵.

[figure not shown]
The source of PFS event (progression or death) will be summarized by treatment group.

[figure not shown]
Analyses of PFS may also be conducted based on the secondary definition of PFS. These analyses will be the same as those specified above.

The status of subjects who are censored (as per primary definition of PFS) in the PFS KM analysis will be tabulated for each randomized treatment group including the following categories:

- On-study (on-treatment, in follow-up)
- Off-study (lost to follow-up, withdraw consent, never treated)
- No baseline tumor assessment
- No on-study tumor assessment and no death
- Received subsequent anticancer therapy

Similar analyses will be repeated based on the investigator's assessment of progression.

[figure not shown]
7.5.7 Analysis of Overall Survival

[figure not shown]
One of the objectives of the study is to assess the difference in overall survival between treatment groups in each of the randomized populations.

Overall survival will be compared between the treatment groups, using stratified log-rank test. The stratification factors will be those used in the analysis of PFS. The stratified hazard ratio between the treatment groups will be presented along with 70% CI.

OS will be estimated using the KM techniques. A two-sided 95% CI for median OS in each treatment group will be computed via the log-log transformation method. OS rates at fixed time points (e.g. 6 months, depending on the minimum follow-up) will be presented along with their associated 95% CIs. These estimates will be derived from the Kaplan Meier estimate and corresponding CIs will be derived based on Greenwood formula for variance derivation and on log-log transformation applied on the survivor function.

The status of subjects who are censored in the OS KM analysis will be tabulated for each treatment group using the following categories:

- On-study (on-treatment, in follow-up)
 - Off-study (lost to follow-up, withdraw consent, never treated)
- 

7.5.8 Current Status of PFS and OS Follow-up

The extent of follow-up for survival, defined as the time between randomization date and last known alive date (for subjects who are alive) or death date (for subjects who died), will be summarized descriptively (median, min, max) in months for all randomized populations.

The currentness of follow-up for survival, defined as the time between last OS contact (i.e., last known alive date or death date) and cutoff date (defined by last patient last visit date), will be summarized in months for all randomized subjects. Subjects who died and subjects with last known alive date on or after data cut-off date will have zero value for currentness of follow-up.

Minimum follow-up for OS, defined as the time from cutoff date to last subject's randomization date, will be summarized in months for all randomized subjects.

Time from last evaluable tumor assessment to cutoff date in months will be summarized by treatment group and overall for all randomized subjects. Subjects who have a PFS event will be considered as current for this analysis. The secondary definition of PFS will be used for this summary.

By-subject listing will also be produced to accompany the subject time from last evaluable tumor assessment.

7.5.9 Interim analysis of Overall Survival

Interim analysis for OS will be performed at the time of the primary database lock.

7.6 Safety

Analyses in this section will be tabulated for all treated subjects by treatment group as treated, unless otherwise specified.

7.6.1 Deaths

Deaths will be summarized by treatment group. These analyses will be performed on the All Treated LAG-3 Positive Subjects, All Treated LAG-3 Negative Subjects, and All Treated Subjects.

- All deaths, reasons for death
- Deaths within 30 days of last dose received, reasons for death
- Deaths within 100 days of last dose received, reasons for death

A by-subject listing of deaths will be provided for the all enrolled subjects population.

